6.2.2.1 Visit 1 – Baseline Visit

Upon patient enrollment, the following will be recorded on the patient's eCRF.

- Visit date
- Diagnosis: date of the diagnosis and the diagnostic procedures performed
- Inclusion / exclusion criteria
- Demographic data: date of birth, gender, pregnancy, previous allergy, height, weight
- Renal function: record creatinine clearance collected within at least one year prior to enrolment
- Lifestyle factors: smoking habits and alcohol use
- Atrial fibrillation disease characteristics: categorization, type, procedures since confirmation of AF diagnosis
- Medical history: history of thromboembolic episodes, cardiovascular diseases, history of bleeding events, other relevant medical history
- Anti-thrombotic therapy: record all the anti-thrombotic therapy received since one month prior to the baseline visit (excluding Pradaxa)
- Concomitant medications: record all medications as well as continuous medications since one month prior to the baseline visit except for anti-thrombotic therapy (but including vitamins and food supplements)
- Dose of Pradaxa given
- Vital signs: average blood pressure (sitting arm) and pulse rate

At Visit 1, the patient will be requested to contact the treating physician in the event of any adverse events noted after initiating Pradaxa treatment.

6.2.2.2 Visit 2 (12 \pm 2 weeks from Visit 1)

After 12 \pm 2 weeks from Visit 1, the patients will return for follow-up. The followings will be noted and recorded in the eCRF:

Proprietary confidential information. © 2014 Boehringer Ingelheim International GmbH or one or more of its affiliated companies.

- Visit date
- Any change of Pradaxa dose given
- Any changes in laboratory tests which required actions on drug dosage since last visit or any laboratory values performed to monitor the increased risk of bleeding ie. aPTT
- Vital signs: average blood pressure (sitting arm) and pulse rate
- Effectiveness endpoints: incidence of stroke or systemic embolism
- Anti-thrombotic therapy: any change in the anti-thrombotic therapies since last visit (excluding Pradaxa)
- Concomitant medications including new medications taken since last visit: any change in the concomitant medications (dose and dosing intervals)
- Any adverse events noted
- Treatment compliance
- **Study completion status: for the prematurely withdrawn patients, this section should be recorded to assess the safety information and the reason for withdrawal**
- NIS physician's electronic signature for data integrity (do not record this section for long-term FU cases)

At Visit 2, the patients on long-term follow-up will be reminded to contact the NIS physician in the event of any adverse events noted hereafter.

6.2.2.3 Visit 3 (24±2 weeks from Visit 1, Long-term follow-up cases only)

After 24±2 weeks from Visit 1 or 12±2 from Visit 2, the patients will return for follow-up. The followings will be noted and recorded in the eCRF:

- Visit date
- Any change of Pradaxa dose given
- Any changes in laboratory tests which required actions on drug dosage since last visit or any laboratory values performed to monitor the increased risk of bleeding ie. aPTT
- Vital signs: average blood pressure (sitting arm) and pulse rate
- Effectiveness endpoints: incidence of stroke or systemic embolism
- Anti-thrombotic therapy: any change in the anti-thrombotic therapies since last visit (excluding Pradaxa)
- Concomitant medications including new medications taken since last visit: any change in the concomitant medications (dose and dosing intervals)
- Any adverse events noted
- Treatment compliance
- **Study completion status: for the prematurely withdrawn patients, this section should be recorded to assess the safety information and the reason for withdrawal**
- NIS physician's electronic signature for data integrity

6.2.3 End of trial and follow-up period

For patients prematurely withdrawn from the study, it is important to collect the safety information whether or not any adverse event occurred after administration of Pradaxa and reflect the information in the eCRF section of "study completion status". Patients with adverse events noted at the final follow-up visit or upon premature discontinuation of Pradaxa will be monitored further until the resolution of those adverse events. Alternatively, those

Proprietary confidential information. © 2014 Boehringer Ingelheim International GmbH or one or more of its affiliated companies.

patients will be followed up until the NIS physician and sponsor agree that no further follow-up is necessary. To the extent possible, vital status, at minimum, for patients lost to follow up will be obtained.

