3.2 DISCUSSION OF STUDY DESIGN

This is a single arm study with dabigatran etexilate mesilate cohort.

Loss to follow up

All efforts will be made to minimize loss to follow up, particularly in the tracking of lost patients. To the extent possible, vital status, at minimum, for patients lost to follow up will be obtained. This allows assessing the impact of informative censoring due to treatment discontinuation. Also, patients lost to follow up will be characterized compared to the remaining patients and reason and time point of loss to follow up will be evaluated.

Channeling bias

Channeling bias can occur due to preferential prescribing in relation to different risks for the events of interest: e.g., if dabigatran would be more often prescribed to higher risk patients compared to other treatments, higher incidences of outcome events were then expected in the dabigatran group.

Information and recall bias

Information bias can e.g. occur due to selective reporting of already established and known adverse effects for a known product as compared to a new product (dabigatran), or vice versa. A standardized data collection form will be used for assessing exposure and AEs. These standardized procedures for data collection are intended to minimize such biases. Recall bias may be caused, e.g. if visits are separated by long time intervals and patient forget certain information. It can be reduced by associating questions with specified time intervals (e.g. how often did you take this co-medication *during the last 5 days*).

Proprietary confidential information. © 2014 Boehringer Ingelheim International GmbH or one or more of its affiliated companies.

Confounding

As in any observational study, confounding may affect the estimation of association between drug exposure and outcome of interest and statistical techniques. However, as only major confounders for selected research questions can be captured, residual (unmeasured) confounding may remain.

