3.3.4 Removal of patients from therapy or assessments

3.3.4.1 Removal of individual patients (therapy or assessments)

This section is not applicable.

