7.3 PLANNED ANALYSES

7.3.1 Primary analyses

A descriptive analysis of effectiveness endpoints is planned. For patients treated with Pradaxa incidence of stroke or systemic embolism will be calculated. Effectiveness analyses will be performed based on demographics and baseline characteristics. However, if data for patients who have been treated with Pradaxa beyond the scope of approved label are collected, separate effectiveness analyses will be conducted.

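### The protocol does not say that a patient who stops Pradaxa early stays under observation to week 12 or 24, so follow-up after the stop is left to the site

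*Combined protocol and SAP*

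**What the plan says.** **After an early stop.** Section 6.2.3: "Patients with adverse events noted at the final follow-up visit or upon premature discontinuation of Pradaxa will be monitored further until the resolution" of those events, or until physician and sponsor agree that no more follow-up is needed. Nothing is stated for a patient who stops without an adverse event.

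**After withdrawal from the study.** Section 6.2.3: "For patients prematurely withdrawn from the study, it is important to collect the safety information whether or not any adverse event occurred". The visit lists in 6.2.2.2 and 6.2.2.3 add, under study completion status, "for the prematurely withdrawn patients, this section should be recorded to assess the safety information and the reason for withdrawal". Neither place names stroke or embolism status or the next antithrombotic.

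**After loss to follow-up.** "To the extent possible, vital status, at minimum, for patients lost to follow up will be obtained" (6.2.3). Of this vital-status effort, section 3.2 says: "This allows assessing the impact of informative censoring due to treatment discontinuation".

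**The rule that would tell these groups apart.** Section 3.3.4.1 covers removal from therapy or from assessments. Its whole content is "This section is not applicable".

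**What is analysed.** Section 7.3.1: "For patients treated with Pradaxa incidence of stroke or systemic embolism will be calculated". Section 5.1.2 limits the effectiveness analysis to patients on Pradaxa for more than 12 weeks (24 in the long-term group). Section 7.3.3 bases safety on everyone with at least one dose and compares patients lost to follow-up with those remaining.

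**The concern.** Three different situations need three different instructions: the patient stops the drug, the patient leaves the study, and the patient cannot be reached. The protocol gives partial instructions for each but never says that the first does not imply the second. Section 6.2.2 describes follow-up as a treatment period, and section 3.2 links stopping treatment with censoring, so a site could reasonably close a patient out when the drug stops.

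Stopping is unlikely to be unrelated to outcome. By the intensity definitions in 5.2.2.1, a severe adverse event is one that requires the drug to be stopped, and adverse events leading to discontinuation are a safety endpoint in 5.2.1. If observation ends at the stop in some patients, the missing time is selected. Vital status cannot repair this, because it shows neither a non-fatal stroke nor a change of anticoagulant. Safety is the primary objective (2.2.1), so the question matters even though 5.1.2 disclaims any meaningful effectiveness assessment. Data that were never recorded cannot be recovered by a later choice of analysis set.

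**Working it through.** **1. What two compliant sites could do.** Take a reachable short-term patient who stops part-way with no adverse event and has a stroke before week 12.

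- Site A keeps the patient to Visit 2. Section 6.2.2.2 then records the stroke and any change in antithrombotic therapy. The adverse event window in 5.2.2.2 runs to 7 days after the last follow-up visit, so it covers the stroke as well.
- Site B closes the patient at the stop, with the reason and a statement that no adverse event occurred. If that contact is taken as the last follow-up visit, the window closes 7 days later. A stroke after that need not be recorded, nor need the next antithrombotic.

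No sentence in the protocol makes either site wrong, so observed time after stopping can differ by site.

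**2. Planned observation.** Section 7.6 gives 1,500 short-term and 1,500 long-term patients: 1,500 + 1,500 = 3,000, and 1,500 / 3,000 = 50%, as stated there. With the follow-up lengths in 6.2.2:

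1,500 × 12 + 1,500 × 24 = 54,000 patient-weeks; 54,000 × 7 / 365.25 = 1,034.9 patient-years.

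**3. Time after stopping.** The documents give no stopping rate. Assume a proportion p stops early, the same in both groups, at times uniform over the planned period. Each stopper then has on average half the planned time left, so the time after stopping is (p / 2) × 1,034.9.

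| Assumed p | Patients stopping | Patient-years after the stop | Share of plan |
|---|---|---|---|
| 10% | 300 | 51.7 | 5% |
| 20% | 600 | 103.5 | 10% |
| 30% | 900 | 155.2 | 15% |

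These figures are the time exposed to the gap. Time is lost only where a site ends follow-up at the stop, and the documents do not show how often that would happen.

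**4. Scale in stroke or embolism events (illustration only).** Assume also an on-drug rate of 1 to 2 per 100 patient-years and an off-drug rate 1 to 3 times that. At p = 20%, the events falling after the stop range from 103.5 × 0.01 × 1 = 1.0 to 103.5 × 0.02 × 3 = 6.2. None of these rates is in the documents, and the counts are of events occurring, not of events missed.

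**The case against.** The strongest reply is that no sentence ends participation when Pradaxa stops. A reader might infer from 6.2.3 that stopping is handled as leaving the study, so that stroke or embolism status and the replacement drug are not collected. The documents do not support that:

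- The 6.2.3 sentence extends follow-up for patients with adverse events; it closes nobody out. The sentence before it deals separately with patients withdrawn from the study.
- Visits 2 and 3 record stroke or embolism and antithrombotic changes with no on-drug condition, and the flow chart records Pradaxa administration status at both.
- The adverse event window is tied to the last follow-up visit, not the last dose. A stroke is an adverse event and will usually meet the serious criteria. Section 4.2 has concomitant therapy recorded to the final visit.
- Vital status is sought for patients lost to follow-up, not for stoppers as such.

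Nor does the text support a claim that observation after a bleeding-driven stop is generally cut off: a patient who stops with an adverse event is the one that 6.2.3 follows to resolution. And if the effectiveness incidence describes persisters, the direct cause is the restriction in 5.1.2, not this gap.

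One can also say that a removal rule is not expected in a non-interventional study, and that not applicable may mean stopping triggers no removal. The separate TSAP and the eCRF (Attachment 1) are not in the supplied text and may say more.

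All of this stands against the stronger reading. It does not supply the missing instruction. The protections work only if the patient keeps being seen, and nothing says so for a stopper without an adverse event. A removal section that might be read either way is itself a reason to clarify. Sites need the rule in the protocol, whatever the TSAP contains.

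**Conclusion.** The point holds as a gap in required data collection. Continued observation to week 12 or 24 after an early stop is not stated, and several sections allow close-out at the stop. For withdrawn patients, stroke or embolism status and the next antithrombotic are not asked for. The main consequence is for the all-treated safety analysis in 7.3.3, where observation of stoppers can be shortened in an informative way that varies by site. The comparison of lost with remaining patients leaves reachable stoppers without a category.

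The size is unknown. The range of 52 to 155 patient-years rests on assumed stopping of 10% to 30% at uniform times and is an upper limit on lost time under those assumptions. A percentage of missed events should not be quoted: it would need stopping and event rates that the documents lack, and would assume that no stopper is seen again and no stroke is reported as an adverse event.

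The study is descriptive with no hypotheses (7.1, 7.2), so this is an improvement that should be made because it is cheap; it does not invalidate the plan.

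**What to change.** - **Sections 3.3.4.1 and 6.2.3:** replace the not-applicable entry and state that stopping or switching Pradaxa is not withdrawal from the study. Where data release consent stands, record at the planned week 12 or 24 the Visit 2 or 3 items, adverse events, date of last dose, reason for stopping, and next antithrombotic with its start date. Use the chart or a telephone call if no visit takes place.
- **Sections 6.2.2.2 and 6.2.2.3:** ask for the same items at early withdrawal.
- **Section 7.3.3:** describe three groups: completed on Pradaxa, stopped but followed, and lost.
- **Sections 5.1.2 and 7.3.1:** report stroke or embolism in all treated patients alongside the set on drug for more than 12 (24) weeks. Without this, the added data would not reach the effectiveness result.

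The cost is protocol wording, a few eCRF fields (fewer if the eCRF already holds some of them) and one chart check or call per early stopper. No procedure or patient is added, and no treatment decision changes.

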7. STATISTICAL METHODS AND DETERMINATION OF SAMPLE SIZE

Details are provided in the statistical Trial Statistical Analysis Plan (TSAP).

7.1 STATISTICAL DESIGN - MODEL

In this non-interventional study, all statistical analyses will be descriptive in nature. The degree of statistical significance (p-values) and precision (confidence intervals) for the statistical methods used for explorative purposes will be shown. No confirmatory hypotheses are pre-specified.

7.2 NULL AND ALTERNATIVE HYPOTHESES

No hypotheses are tested. (See Section 7.1)

7.3 PLANNED ANALYSES

7.3.1 Primary analyses

A descriptive analysis of effectiveness endpoints is planned. For patients treated with Pradaxa incidence of stroke or systemic embolism will be calculated. Effectiveness analyses will be performed based on demographics and baseline characteristics. However, if data for patients who have been treated with Pradaxa beyond the scope of approved label are collected, separate effectiveness analyses will be conducted.

7.3.2 Secondary analyses

There is no secondary effectiveness analysis planned in this study. However, additional exploratory analyses will be conducted as deemed appropriate.

7.3.3 Safety analyses

Demographic and baseline characteristics (including specifically stroke/bleeding risk scores (CHADS₂, CHA₂DS₂-VASc and HAS-BLED)) will be summarized descriptively for the entire cohort of eligible patients.

Adverse events (AEs) will be coded according to the latest version of Medical Dictionary for Drug Regulatory Affairs (MedDRA) coding system. Concomitant therapies will be coded according to the latest version of KIMS (Korea Index of Medical Specialties) coding system. The trial database will not be locked until coding is complete.

Safety analyses will be based on all patients treated, i.e. all patients who received at least one dose of Pradaxa. However, if data for patients who have been treated with Pradaxa beyond the scope of approved label are collected, separate safety analyses will be performed. Safety analyses will be performed based on demographics and baseline characteristics.

Proprietary confidential information. © 2014 Boehringer Ingelheim International GmbH or one or more of its affiliated companies.

Patients lost to follow up will be characterized compared to the remaining patients and reason and time point of loss to follow up will be evaluated.

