5.1.2 Assessment of effectiveness

Since the patient follow-up period is only 12 weeks (in case of long-term FU, 24 weeks), it is not possible to perform any meaningful effectiveness assessment of Pradaxa in this NIS. However, since it is a requirement to evaluate also effectiveness in all regulatory requisite NIS in Korea and as requested by **MFDS**, a descriptive analysis of effectiveness endpoint will be performed.

Effectiveness analysis will be performed to the patients who have been on Pradaxa more than 12 weeks (in case of long-term FU, 24 weeks).

The following definitions apply and should be used as a guide when reporting a thrombotic event:

Stroke:

Stroke is an acute onset of a focal neurological deficit of presumed vascular origin lasting for 24 hours or more or resulting in death. The stroke is categorized as ischemic or hemorrhagic or uncertain classification (based on CT or MR scanning or autopsy). Fatal stroke is defined as death from any cause within 30 days of stroke. Severity of stroke will be assessed by modified Rankin Scale (see Table 10.1:4) at discharge from hospital and/or at 3-6 months later (if available).

Systemic embolism:

Systemic embolism is an acute vascular occlusion of the extremities or any organ (kidneys, mesenteric arteries, spleen, retina or grafts), typically documented by angiography, surgery, scintigraphy, or autopsy.

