5.2.2.2 Adverse event and serious adverse event reporting

All adverse events occurring from the start of Pradaxa treatment up to 7 days after last follow-up visit need to be collected, documented and reported to the sponsor using the AE reporting form of eCRF (Attachment 1). All SAEs must be reported with details of non-serious AEs occurring at the same time, within 24 hours of occurrence via telephone/fax to the Clinical Safety Officer (CSO) of BI Korea using the SAE report form (Attachment2). If any new or further information to these events is available, a follow-up SAE report has to be sent to BI. All SAEs and non-serious AEs must include a causal relationship assessment from the physician.

All other Adverse Events must be reported on the eCRFs within 2 weeks to the Sponsor.

Contact details:

Clinical Safety Officer

[contact]

[contact]

Address: Boehringer Ingelheim Korea, Medical Dept.

[name]

Pregnancy

Rarely, patients taking part in non interventional studies can get pregnant. Once a patient enrolled into the study and exposed to Pradaxa becomes pregnant, the NIS physician will stop the drug and report immediately to the sponsor. Drug exposure during pregnancy has to be reported immediately (within 24 hours or next business day, whichever is shorter) to CSO. Furthermore, the details of all the drugs to which the patient exposed at the time of pregnancy will be recorded. The outcome of the pregnancy associated with the drug exposure will be assessed. In the absence of an (S)AE, only the Pregnancy Monitoring Form (Attachment 3) for NIS, not the SAE form is to be completed. The ISF will contain the Pregnancy Monitoring Form (Part A and Part B) and those forms could be downloaded from eCRF website.

Proprietary confidential information. © 2014 Boehringer Ingelheim International GmbH or one or more of its affiliated companies.

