6.2.2 Treatment period(s)

As per regulations, enrolled patients will be followed up for a 12 week or 24 week treatment period. There will be a visit window of ± 2 weeks. To minimize the selection bias at the site level, the goal is to have participating centers reflect a balance between general hospitals and clinics for short-term or long-term surveillances.

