7.6 DETERMINATION OF SAMPLE SIZE

Sample size of 3,000 patients is based on the requirement of the local regulatory authority (Korean FDA). The number of patients enrolled for short-term surveillance will be 1,500 and for long-term follow up 1,500. As per regulation, long-term surveillance is necessary for the indication. It will be conducted to 50% of total number of enrolled patients.

Proprietary confidential information. © 2014 Boehringer Ingelheim International GmbH or one or more of its affiliated companies.

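### Effectiveness is restricted in section 5.1.2 to patients who complete 12 or 24 weeks on drug, against treated patients in 7.3.1, and section 7 gives no time basis for mixed follow-up

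*Combined protocol and SAP*

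**What the plan says.** **Effectiveness.** Section 5.1.1 names the endpoint as an incidence rate of stroke or systemic embolism, without a denominator or unit of time. Section 5.1.2 sets the population: "Effectiveness analysis will be performed to the patients who have been on Pradaxa more than 12 weeks (in case of long-term FU, 24 weeks". Section 7.3.1, the planned analysis of the same endpoint, says "For patients treated with Pradaxa incidence of stroke or systemic embolism will be calculated" and attaches no minimum duration.

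**Follow-up.** Section 6.2.2 says "enrolled patients will be followed up for a 12 week or 24 week treatment period" and "There will be a visit window of ± 2 weeks". Section 6.2.2.3 offers two routes to the last long-term visit: "After 24±2 weeks from Visit 1 or 12±2 from Visit 2, the patients will return for follow-up". Section 7.6 gives the cohort sizes: "The number of patients enrolled for short-term surveillance will be 1,500 and for long-term follow up 1,500".

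**Safety.** Section 7.3.3 says "Safety analyses will be based on all patients treated, i.e. all patients who received at least one dose of Pradaxa". The only breakdowns it names are off-label use and demographic and baseline characteristics. Section 5.2.2.2 sets the collection window: "All adverse events occurring from the start of Pradaxa treatment up to 7 days after last follow-up visit need to be collected".

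**Where the detail sits.** Section 7 refers to a TSAP, which is not among the documents available here. Section 7.1 makes all analyses descriptive, with confidence intervals shown.

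**The concern.** The 5.1.2 rule decides who counts at the start by what happens later. A patient who has a stroke in week 5 and then dies or stops Pradaxa does not reach week 12, so that stroke leaves the stroke figure. Patients who stop for unrelated reasons leave the denominator as well. The result describes people who tolerated and survived treatment, not people who were started on it. Two analysts could also follow the protocol, one using 5.1.2 and the other 7.3.1, and report different figures.

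The second issue is time at risk. By design, one half of the patients is observed for about twice as long as the other. If events are divided by heads across both cohorts, the percentage belongs to no stated period. Subgroups with different shares of long-term patients could then differ for that reason alone. Safety is the primary objective (section 2.2.1), so the meaning of its percentages matters even without a hypothesis test.

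**Working it through.** **1. The plan's own figure.** 1,500 + 1,500 = 3,000, and 1,500/3,000 = 50% long-term. This agrees with section 7.6.

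**2. Who the 5.1.2 rule removes.**
- Anyone who dies or stops at or before week 12 (short-term) or week 24 (long-term). A long-term patient treated for 20 weeks is dropped, while a short-term patient treated for 13 weeks is kept.
- Patients still on drug who are seen early in the window, if exposure is counted from Visit 1 to the final visit (an assumption). The window allows 12 − 2 = 10 to 14 weeks and 24 − 2 = 22 to 26 weeks, so final visits in weeks 10–12 or 22–24 do not exceed the threshold. By the second route in 6.2.2.3, Visit 3 could fall at 10 + 10 = 20 to 14 + 14 = 28 weeks. That does not match 22 to 26, and the two statements need reconciling.

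**3. Size of the completer effect.** Let d be the share of patients, and f the share of event patients, not past the threshold. The documents give neither, so both are assumptions.

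Completer risk ÷ all-treated risk = (1 − f)/(1 − d)

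| | f = 10% | f = 25% | f = 50% |
|---|---|---|---|
| d = 10% | 0.9/0.9 = 1.00 | 0.75/0.9 = 0.83 | 0.5/0.9 = 0.56 |
| d = 20% | 0.9/0.8 = 1.125 (given as 1.12) | 0.75/0.8 = 0.94 | 0.5/0.8 = 0.625 (given as 0.62) |

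The figure is too low when f exceeds d and too high when f is below d. The extremes lie further out: 0 at f = 100%, and 1/(1 − d) at f = 0.

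In absolute terms, assume 2 events per 100 patient-years and 10% non-event discontinuation per 12 weeks. All treated: 20.6/3,000 = 0.69%. Completers: 20.6/2,568 = 0.80% at f = 0, 10.3/2,558 = 0.40% at f = 50%, and 4.1/2,552 = 0.16% at f = 80%.

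**4. Size of the mixed follow-up effect.** Risk by week w at rate r per patient-year is 1 − exp(−r × w/52.18). The pooled n/N is the mean of the 12- and 24-week risks, because the cohorts are equal. Rates are assumptions.

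| Assumed rate | 12 weeks | 24 weeks | Pooled n/N | ÷ 12-week | ÷ 24-week |
|---|---|---|---|---|---|
| 0.015, constant | 0.344% | 0.688% | 0.516% | 1.50 | 0.75 |
| 0.015, half after week 12 | 0.344% | 0.516% | 0.430% | 1.25 | 0.83 |
| 0.015, quarter after week 12 | 0.344% | 0.430% | 0.387% | 1.12 | 0.90 |
| 0.20, constant | 4.5% | 8.8% | 6.6% | 1.48 | 0.76 |

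**5. Knock-on for subgroups.** Take two subgroups with the same hazard but 60% and 40% long-term patients (an assumed mix). At rate 0.015 constant, n/N is 0.6 × 0.688 + 0.4 × 0.344 = 0.550% against 0.4 × 0.688 + 0.6 × 0.344 = 0.482%, a ratio of 1.14. With the later hazard halved or quartered the ratio is 1.08 or 1.05. At 70% against 30% the three ratios are 1.31, 1.17 and 1.09.

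**The case against.** **Section 7.3.3 does not prescribe pooling.** A reader might infer that it commits the sponsor to one pooled percentage. It names an analysis set, and all patients with at least one dose is the conventional one. Time points and cohort tables would normally sit in the TSAP. This stands: the protocol is silent on the time basis, and the finding goes no further.

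**Events after stopping are not ignored.** A reader might infer that they go uncounted. Section 5.2.1 covers all reported adverse events after one dose, 5.2.2.2 sets no on-drug condition, 6.2.3 collects safety data on withdrawn patients, and 7.4 uses all available data. These point to inclusion. What remains unstated is the denominator.

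**Strokes are not lost.** A stroke removed by 5.1.2 still meets the adverse event definition and enters the safety set. Section 5.1.2 itself says that no meaningful effectiveness assessment is possible and that the analysis is done because the regulator asks for it. This lowers the stakes, but a figure that will be reported still needs one defined population.

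**The two sections could be read together,** with 7.3.1 subject to 5.1.2. That removes the conflict only by making the completer set the sole effectiveness set.

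**Subgroup imbalance is assumed.** Section 6.2.2 aims for a balance of general hospitals and clinics, and no document figure supports a 70/30 mix. This stands. That balance concerns type of site, not patient characteristics.

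**Conclusion.** The effectiveness point holds on the text alone: 5.1.2 and 7.3.1 describe different populations, and the 5.1.2 rule conditions on completing treatment. Its size does depend on assumptions: 0.56 to 1.12 times the all-treated risk for d of 10–20% and f of 10–50%. A reader might infer that the rule necessarily understates stroke risk. The documents do not support that, because they do not say who stops or why. Understatement follows only if patients with events are over-represented among those removed.

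The time-basis point is secondary and conditional. If the TSAP does not say otherwise, nothing in section 7 prevents 12- and 24-week follow-up from being mixed in one percentage, about 1.5 and 0.75 times the two risks at constant hazard and closer to both if events cluster early. No confirmatory test, error rate or sample size is affected. Both points should be corrected; neither invalidates the study.

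**What to change.** 1. In 5.1.2 and 7.3.1, make all patients with at least one dose the main effectiveness set, and keep the 5.1.2 set as supplementary only.
2. In 7.3.1 and 7.3.3, report stroke or systemic embolism and the main adverse event tables as 12-week incidence in all treated patients and 24-week incidence in the long-term cohort, with 95% CI. Permitted final visits start at week 10, so censor at last contact. At the least, split n/N tables by surveillance cohort as fixed at enrolment. Patient-year rates may be added. Competing-risk estimates for every adverse event category are not needed.
3. In 5.1.1, state the denominator of the incidence rate. If the TSAP already covers these items, cite it in section 7.
4. Reconcile the two routes to Visit 3 in 6.2.2.3 with the window in 6.2.2.

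**Cost.** A few lines of text, a few more tables and possibly one baseline field: 6.2.2.1 lists no cohort item, although the eCRF was not available and may hold one. Visit dates, event onset dates (8.4.2) and time of loss to follow-up (7.3.3) are already planned.

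**Precision.** At an assumed 1.5 events per 100 patient-years with complete follow-up, 3,000 × 0.344% and 1,500 × 0.688% each give 10.3 expected events. Exact 95% intervals are 0.16% to 0.61% for 10/3,000 and 0.32% to 1.22% for 10/1,500.
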